**Is there any additional aspect you would like to propose to improve the management of SCD?**

---

---

---

---

## Annex II. QUESTIONNAIRE FOR NEED ASSESSMENT OF HEALTH WORKERS INVOLVED IN SICKLE CELL DISEASE MANAGEMENT

Questionnaire code: \_\_\_\_\_

### SECTION A - Bio Data

1. State \_\_\_\_\_

2. Local Government \_\_\_\_\_

3. Name of SCD Clinic/Hospital \_\_\_\_\_

4. Age \_\_\_\_\_

5. Gender Male [ ] Female [ ]

6. Please indicate your area of specialization

- A. Medical Doctor [ ]
- B. Nurse [ ]
- C. Laboratory technology [ ]
- D. Pharmacist [ ]
- E. Others (please specify) \_\_\_\_\_

7. Average weekly effective working hours \_\_\_\_\_

### SECTION B

**1. Which of the following additional training did you receive on Sickle Cell Disease management in the past three months?**

- A. Seminar [ ]
- B. Conference [ ]
- C. Workshop [ ]
- D. Training [ ]
- E. None of the above [ ]
- F. Other (please specify) \_\_\_\_\_

**2. How often do you see or attended to Sickle Cell Disease patients?**

- A. Once in a week [ ]
- B. Twice in a week [ ]
- C. Once in a month [ ]
- D. Twice in a month [ ]
- E. Other (please specify) \_\_\_\_\_

**3. How many Sickle Cell Disease patients do you see or attend in the clinic?**

- A. 5-10 [ ]

B. 10-15 [ ]  
C. 15-20 [ ]  
D. Other (please specify) \_\_\_\_\_

**4. How many SCD patients do you think is adequate for you to see or attend?**

A. 5-10 [ ]  
B. 10-15 [ ]  
C. 15-20 [ ]  
D. Other (please specify) \_\_\_\_\_

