## 3. Objectives

### 3.1. Primary objective

To assess the needs of SCD patients and health workers, with particular reference to the disease management in the clinical centre.

The study is intended as a pilot experience to verify the feasibility of the action through a structured survey. This is a descriptive, mixed method prospective questionnaire-based study. The study is intended as a pilot experience to verify the feasibility of the action through a structured survey.

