### 3.2. Sample size determination

As pilot experience, the questionnaires will be administered to 30 SCD patients or parents/legally designated representatives of children affected by SCD and 30 Professionals working with SCD patients (mainly doctors and nurses) in each centre for a total of 120 patients and 120 health workers. A focus group discussion will be run with the SCD patients/parents. Following the pilot study, a wider survey will be launched involve patients, parents and healthcare professionals in the whole country and in other centres involved in the project.

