### 3.3. Setting

The study will be conducted in the following four centres: Barau Dikko Teaching Hospital Kaduna State University (BDTH), Ahmadu Bello University Teaching Hospital Zaria (ABUTH), National Hospital Abuja (NHA), and Federal Medical Centre Katsina (FMC).

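### Annex II items 3 and 4 take patient numbers from 5 to 20 in the same five-wide, overlapping bands with no time unit, so many small differences between actual and adequate load cannot be seen

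*Protocol*

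**What the plan says.** Annex II, Section B, item 3 asks "How many Sickle Cell Disease patients do you see or attend in the clinic". Item 4 follows directly and asks "How many SCD patients do you think is adequate for you to see or attend". The answer options are identical: 5-10, 10-15, 15-20, and "D. Other (please specify" with a blank for free text. Each band prints both of its ends, so 10 belongs to the first and second bands and 15 to the second and third. Neither item says whether the count is per clinic session, per day or per week.

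The items serve the primary objective in Section 3.1: "To assess the needs of SCD patients and health workers, with particular reference to the disease management in the clinical centre". The same section describes the design: "This is a descriptive, mixed method prospective questionnaire-based study". Section 3.2 plans 30 health workers "in each centre for a total of 120 patients and 120 health workers", as a pilot before a wider national survey. Section 5.4 names SPSS and thematic analysis and does not say how items 3 and 4 will be used. Elsewhere on the same form, age and average weekly working hours (Section A, items 4 and 7) are written in as numbers.

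**The concern.** Item 4 says little about need on its own. Its evident use is beside item 3: does the worker see more SCD patients than he or she considers adequate, and by how many? With shared bands, a difference appears only when the two numbers fall on different sides of a band edge. A wish for two or three fewer patients can vanish, and a wish for one fewer can appear as a full band.

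No other item replaces the pair. Weekly hours are not SCD load. Work overload is offered as a reason only to staff who answer No to item 17. Item 18 is open text.

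At stake is whether the pilot can give the size of any load difference, and whether an answer format with this limit is carried into the wider survey. Choices made at analysis cannot help, because once a band is ticked the number is gone.

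**Working it through.** **Inputs from the protocol.** Bands 5-10, 10-15 and 15-20 in both items (Annex II, Section B, items 3 and 4); 30 health workers per centre (Section 3.2); four centres (Section 3.3).

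**The plan's own figure.** 30 × 4 = 120 health workers, as stated. The protocol gives no figure for a load difference, and no power calculation applies to a descriptive pilot.

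**What a pair of ticks can mean.**
- Same band twice: the true difference (seen minus adequate) can be anything from -5 to +5. With 5-10 ticked twice, the extremes are 5 - 10 and 10 - 5.
- 10-15 seen, 5-10 adequate: the true difference can be anything from 10 - 10 = 0 to 15 - 5 = 10.
- Clean example: sees 14, thinks 11 adequate. Both numbers belong only to 10-15, so a difference of 3 shows as none.

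**Share of differences that do not show.** Let x be the number seen and d the number of patients fewer that is wanted. The even spread of x is an assumption; the documents give no distribution.

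1. *Whole numbers, both answers within 5-20.* Put 10 and 15 in the upper band. The bands then hold 5, 5 and 6 values, and same-band pairs number (5 - d) + (5 - d) + (6 - d) = 16 - 3d out of 16 - d possible pairs. Putting 10 and 15 in the lower band, or splitting them at random, gives the same shares for d = 1 to 4.
2. *Whole numbers, x from 5 to 20, adequate numbers below 5 written in.* (16 - 3d)/16.
3. *Whole numbers, x from 10 to 20.* By count, 9, 7, 5 and 3 of 11.
4. *Continuous x from 10 to 20.* 1 - d/5.
5. *Continuous, both answers within 5-20.* 3(5 - d)/(15 - d).

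| d | (1) | (2) | (3) | (4) | (5) |
|---|---|---|---|---|---|
| 1 | 13/15 = 87% | 13/16 = 81% | 9/11 = 82% | 80% | 86% |
| 2 | 10/14 = 71% | 10/16 = 63% | 7/11 = 64% | 60% | 69% |
| 3 | 7/13 = 54% | 7/16 = 44% | 5/11 = 45% | 40% | 50% |
| 4 | 4/12 = 33% | 4/16 = 25% | 3/11 = 27% | 20% | 27% |

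Under (1), over d = 1 to 4 together, (13 + 10 + 7 + 4)/(15 + 14 + 13 + 12) = 34/54 = 63% do not show.

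**The overlap.** Because both ends are printed, a difference of 5 (10 to 5, 15 to 10, 20 to 15) can also be hidden, in 9-11% of pairs with that difference. In the other direction, a worker whose two numbers are both 10, or both 15, and who picks a box at random each time shows a false difference half the time. With x spread evenly over 5-20, that is 2 × 0.5/16 = 6% of staff who have no difference.

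**Dependence on the share within 5-20.** If a share p of staff have both numbers in that range, the hidden share is p times the figures in (1). For d = 3 this is 54% at p = 1 and 27% at p = 0.5.

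**The case against.** The strongest reply has four parts.

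*The bands are not the whole answer format.* This is correct. Both items have a write-in option, so a number below 5 or above 20 is not lost. A reader might infer that load is recorded only in bands; the form does not support that. When just one of the two numbers is written in, the difference shows but its size stays vague: 4 written against 5-10 ticked means anything from 1 to 6.

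*The protocol never says the items will be compared.* Also correct. A reader might infer that a planned estimate of excess workload is biased towards zero. No such estimate is defined, and the overlap at 10 and 15 can create differences as well as hide them. Two separate band distributions are a legitimate descriptive output, and an analysis plan not shown here may settle the use of the items. What remains is that no analysis plan can restore numbers that were never collected.

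*Workload can surface elsewhere.* Partly so. Hours, the overload reason and the open item 18 may reveal it as a theme, so the form does not rest on this pair alone to detect it. None of them gives an actual count against an adequate count.

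*Written numbers will be rounded.* This is a fair point. If staff round to fives, small differences are lost anyway. But rounding then depends on the respondent, whereas the bands impose the loss on everyone within 5-20.

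**Conclusion.** The point holds as a limit of the answer format. For staff whose two numbers lie within 5-20, a comparison of items 3 and 4 would miss about 80-87% of wishes for one fewer patient, 60-71% for two, 40-54% for three and 20-33% for four. It would also give arbitrary results at exactly 10 and 15. Missed differences are the majority for one or two patients, about half for three, and a minority for four, so it would be too strong to say that differences of four usually disappear.

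These shares rest on an even spread of loads and on a comparison inferred from the paired wording. The share of staff within 5-20 is not in the documents, and the impact falls in proportion to it. The missing time unit is a separate fault that applies to all answers: numbers per session and per week could be mixed between items, professions or centres. No stated decision depends on a difference of one to four patients. This is therefore a worthwhile, inexpensive improvement to a pilot questionnaire and does not undermine the study.

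**What to change.** In Annex II, Section B, replace the bands in items 3 and 4 with a written number in one stated time unit, the same in both items, for example: *Number of patients per clinic day: ____*. This removes the band loss, the overlap at 10 and 15 and the missing unit together. Adding a unit while keeping the bands would cure only the last of these.

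State in Section 5.4 or the analysis plan that the within-person difference (item 3 minus item 4) will be reported as median, range and share above zero. Bands can be formed afterwards for display, without shared edges.

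The cost is two answer lines and one sentence on analysis. Age and weekly hours are already written in on the same form, so the format is not new to respondents. The small downside is that some answers will be estimates rounded to convenient numbers; the report should say so.

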**5. How satisfied are you with the relationship you have with the patients?**

A. Very satisfied [ ]  
B. Satisfied [ ]  
C. Neither satisfied Nor dissatisfied [ ]  
D. Dissatisfied [ ]  
E. Very Dissatisfied [ ]

**6. At the clinic, do you educate patients with SCD on self-management aspect of their disease? If yes, what type of information do you give them?**

A. Information about how to avoid complication [ ]  
B. Information about pain management [ ]  
C. Information about symptom [ ]  
D. Other (please specify) \_\_\_\_\_

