## 5. Study procedure

### 5.1. Questionnaire completion

After obtaining the informed consent, subjects (patients, parents/legally designated representatives and healthcare professionals) will be asked to complete the questionnaire. Two questionnaires have been developed, one addressed to patients, parents, legally designated representatives (Annex I) and another one for healthcare professionals (Annex II)

The following measures will be adopted to reduce the interviewer effect:

- The investigator will give instructions to complete, but questionnaires will be self-completed.
- Participants will have time to complete the questionnaire in a private setting.
- Completed questionnaires will be blindly deposited in a closed box. This will be thus safeguarded by the investigators.
- Completed questionnaires will be returned to the coordinating investigator for analysis.

Questionnaires will be pseudonymised: an alphanumeric code will be indicated on each questionnaire and reported on the corresponding informed consent form.

All the study investigators are researchers/officers in the centres not involved in patients' clinical management. The veracity and consistency of responses are of paramount importance for the

---

validity of the study and the improvement of the management of SCD patients: all the actions necessary to allow the participants to freely express themselves will be adopted.

Together with the questionnaire, participants will receive information about the time and venue for the focus group discussion (Annex III). For those who are willing, reminders about the focus group will be sent by e-mail/phone.

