**11. Do you feel protected from injuries and professional risks?**

- A. Very good [ ]
- B. Good [ ]
- C. Neither good nor poor [ ]
- D. Poor [ ]
- E. Very poor [ ]

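### Annex II item 6 has no box for No, so staff who do not teach self-management cannot be told apart from staff who skipped the item

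*Protocol*

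**What the plan says.** Protocol, Annex II, Section B, item 6 puts two questions to the health worker in one item: "do you educate patients with SCD on self-management aspect of their disease? If yes, what type of information do you give them". The printed answers run from "A. Information about how to avoid complication" through pain management and "C. Information about symptom" to a free-text Other. The lettering A to D is continuous, so no option appears to have been lost in reading the file. The item does not say whether more than one box may be ticked.

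On completion, Protocol section 5.1 states: "The investigator will give instructions to complete, but questionnaires will be self-completed". Completed forms go unseen into a closed box and are sent to the coordinating investigator. Each form carries a code that also appears on the consent form, but no step for checking completeness or querying a missing answer is described.

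The number of respondents comes from Protocol section 3.2, which plans "30 Professionals working with SCD patients (mainly doctors and nurses) in each centre for a total of 120 patients and 120 health workers", and from section 3.3: "The study will be conducted in the following four centres".

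Two other items matter here. In Annex I, item 22 asks patients and parents whether they have to go to other centres and lists only kinds of visit or test plus Other; item 23 then opens with a condition on a yes. In Annex II, item 11 asks "Do you feel protected from injuries and professional risks" and offers a five-point rating whose middle category is "C. Neither good nor poor".

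**The concern.** The stem of item 6 allows for a negative answer, since its second half applies only if the first is answered yes. The form gives that negative answer no box. A worker who does not educate patients has no natural way to say so, and on a self-completed form the likely result is a blank. Someone who overlooked the item also leaves a blank. Genuine No answers and item non-response are therefore confounded.

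A No is a plausible answer. The respondent types in Annex II, Section A include laboratory staff, pharmacists and others as well as doctors and nurses, and some of these may have no teaching role.

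At stake is one descriptive result: the proportion of staff who teach self-management. It bears on the primary objective, which concerns needs with emphasis on how the disease is managed in the centre. The study is also a trial run of the survey, and section 3.2 announces a wider one. If the same form is reused, the ambiguity goes with it.

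**Working it through.** **1. The plan's own denominator.** 30 health workers per centre (section 3.2) × 4 centres (section 3.3) = 120. This reproduces the stated total.

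**2. What the item identifies.** Let N = 120 be the forms returned, b the number with item 6 blank, and t = N − b the number with at least one tick. Take any tick to imply Yes. Let q be the unknown fraction of blanks that mean No, and treat the remaining blanks as educators who skipped the item. Then

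share who educate = (N − q·b) / N.

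The form gives N and b but nothing about q, which can lie anywhere from 0 to 1. So:

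- lower bound (q = 1, every blank is a No): t / N
- upper bound (q = 0, every blank is a skipped Yes): N / N = 100%
- blanks dropped as missing: t / t = 100%, whatever b is
- distance between the bounds: b / N

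**3. Numbers.** The protocol gives no expected number of blanks, so b is assumed over a range:

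| Blanks b (assumed) | Ticked t | Lower bound t/120 | Upper bound | Gap b/120 |
|---|---|---|---|---|
| 6 | 114 | 95% | 100% | 5 points |
| 12 | 108 | 90% | 100% | 10 points |
| 24 | 96 | 80% | 100% | 20 points |
| 36 | 84 | 70% | 100% | 30 points |

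As an intermediate case, with b = 24 and half the blanks meaning No, the share is (120 − 12)/120 = 90%. The same data would be compatible with 80% or 100%.

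**4. Comparison with other items in the same protocol.** Annex II item 1 (recent training) includes a none-of-these option. Annex II item 17 records Yes or No before asking for reasons. Annex I item 21 tells the respondent that several boxes may be ticked. Item 6 has none of these features, so it departs from the questionnaires' own practice.

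**5. The parallel item.** Annex I item 22 has the same structure: a yes/no stem, options that fit only a Yes, and an If-yes follow-up in item 23. A tick in item 23 would reveal a Yes, but if both are blank the respondent either does not travel elsewhere or skipped both. The bounds in step 2 apply again, with 120 patients or parents as the denominator.

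**The case against.** Much can fairly be said against reading too much into this.

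- **The share is bounded.** A reader might infer that nothing can be learned about how many staff educate. That goes too far: every tick implies a Yes, so the ticks give a valid lower bound. A respondent could also write none under Other, although that line reads as asking for another type of information. The investigator's instructions could explain this, but no such instruction is recorded.
- **Blanks stay visible.** A reader might infer that the form would report no non-educators at all. The documents do not support this. The blanks would appear in the tabulation, and 100% results only if the analyst drops them or counts them all as Yes.
- **Education gaps can surface elsewhere.** A reader might infer that an unmet need for education could not appear in the study. It could: Annex I item 5 asks about satisfaction with communication on the disease and its treatment, item 9 about instruction on pain control, and there is a closing open question and a focus group. None of these gives the share of staff who educate, but the need is not hidden.
- **Sampling margins.** It is tempting to compare the gap with a confidence-interval half-width at 120. That would assume simple random sampling, whereas section 3.4 describes random and purposive selection and the staff are grouped in four centres. No such margin is used here.
- **An analysis plan may set a rule for blanks.** It may, but a coding rule is a choice of q. It does not supply the missing information.
- **Item 11 is not the same fault.** Its stem and scale do not match in wording, but the five ordered categories cover the full range and can be tabulated. No answer is lost.

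What stands is that, for item 6, a No and a skipped answer cannot be separated, and analysis cannot correct this afterwards.

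**Conclusion.** The point holds in a limited form. The share of staff who teach self-management is not identified from Annex II item 6 without an assumption about blanks; only a lower bound is. For an assumed 6 to 36 blanks among 120 forms, that share lies between 95% and 100% at one end of the range and between 70% and 100% at the other. This rests on all 120 forms being returned, on a tick meaning Yes, and on the assumed number of blanks. If few forms are blank, the ambiguity is small.

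Annex I item 22 has the same defect. Item 11 is a minor wording matter. No hypothesis, sample size or main conclusion depends on item 6, so this is a modest fault in a descriptive pilot. It is still worth correcting, because it lies in the instrument and the repair is very cheap.

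**What to change.** Split Annex II item 6 in two:

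- **6a:** does the respondent teach patients with SCD about self-management? Yes [ ] No [ ]
- **6b:** if yes, which information is given? Keep the current options and state that all that apply may be ticked.

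The share is then Yes / (Yes + No), with blanks in 6a reported separately as non-response.

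Treat Annex I item 22 in the same way: a Yes/No box first, then the list of reasons, with item 23 following only a Yes. If the form is being edited anyway, reword the stem of Annex II item 11 as a request for a rating, so that it fits its scale.

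The cost is one extra tick box per split item; the planned 120 respondents per group do not change. If forms in the present layout have already been completed, report the counts of ticked, written-in none and blank answers, and give both bounds in place of a single percentage.

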**7. How adequate are the number of facilities in the clinic/lab?**

A. Very adequate [ ]  
B. Adequate [ ]  
C. Neither adequate nor inadequate [ ]  
D. Inadequate [ ]  
E. Very inadequate [ ]

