**8. How good are the facilities provided to manage SCD patients?**

A. Very good [ ]  
B. Good [ ]  
C. Neither good nor poor [ ]  
D. Poor [ ]  
E. Very poor [ ]

---

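### Annex II item 7 asks staff for one adequacy rating covering both the clinic and the laboratory, so the answer cannot say which of the two is short

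*Protocol*

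**What the plan says.** Annex II, Section B, item 7 reads "How adequate are the number of facilities in the clinic/lab". It offers one set of five answers from very adequate to very inadequate, with "Neither adequate nor inadequate" in the middle. It has no separate line for each place and no option for someone who does not know or does not use one of them.

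The next item, "How good are the facilities provided to manage SCD patients", rates quality overall and names no place. Item 9 is a free-text line for those who see problems with the facilities.

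One form serves every profession. Section A item 6, "Please indicate your area of specialization", lists doctors, nurses, "Laboratory technology", pharmacists and others. Section 3.2 plans "30 Professionals working with SCD patients (mainly doctors and nurses) in each centre" and sets no number per profession. Section 3.4 gives the sampling strategy as random and purposive, without stratification by profession.

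Section 3.1 makes the needs of patients and health workers the primary objective, with attention to how the disease is managed in the centre.

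**The concern.** The item is double-barrelled: it puts two objects under one rating. The clinic and the laboratory can differ in what they have, and a respondent may know one well and the other hardly at all. Someone who holds different views of the two must choose between them, average them or fall back on the midpoint, and the form does not record which was done.

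What is at stake is how useful the answer is. A shortage of facilities is one of the needs the study sets out to find, and its location decides what a centre would do about it. Because the wording is fixed in the protocol's own annex, no analysis plan can separate two ratings that were collected as one. Section 3.2 also foresees a wider survey after the pilot, into which the item could be carried unchanged.

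**Working it through.** **Step 1. Who answers.** Section 3.2 gives 30 professionals per centre and Section 3.3 names four centres: 30 × 4 = 120. This reproduces the stated total ("for a total of 120 patients and 120 health workers"). The split by profession within the 30 is not fixed.

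**Step 2. What the item can record.** There are four possible opinions:

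| Clinic | Laboratory | Accurate answer on item 7? |
|---|---|---|
| adequate | adequate | yes |
| inadequate | inadequate | yes |
| adequate | inadequate | none |
| inadequate | adequate | none |

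The midpoint does not cover the last two rows. It expresses a neutral view of one thing, not opposite views of two. Two respondents with the same mixed view may therefore tick different boxes, and a respondent in row 3 may tick the same box as one in row 4.

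**Step 3. Whether the place can be recovered from the item.** The protocol gives no expected frequencies, so the shares here are assumptions. Let p_c and p_l be the proportions who find the clinic and the laboratory inadequate, and let w be the share of respondents who have the laboratory in mind. Then

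observed share inadequate = (1 − w) × p_c + w × p_l.

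With w = 0.5:

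- p_c = 20%, p_l = 80%: 0.5 × 20% + 0.5 × 80% = 50%
- p_c = 50%, p_l = 50%: 50%
- p_c = 80%, p_l = 20%: 50%

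Three different situations give one reading. The formula has three unknowns and the item supplies one number.

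If instead everyone considers both places, the reading depends on how they combine them. Take 20% and 80% again. If people answer inadequate when either place is short, the share lies between 80% and 20% + 80% = 100%. If they do so only when both are short, it lies between 20% + 80% − 100% = 0% and 20%. The form does not say which rule applies.

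**Step 4. Staff mix.** Suppose laboratory staff rate the laboratory and everyone else the clinic, with p_c = 20% and p_l = 80%. With 3, 6 or 10 laboratory staff among 30:

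- (27 × 20% + 3 × 80%) / 30 = 26%
- (24 × 20% + 6 × 80%) / 30 = 32%
- (20 × 20% + 10 × 80%) / 30 = 40%

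In general the shift between two centres with the same facilities is (difference in w) × (p_l − p_c). Going from 10% to 30% laboratory staff moves the pooled figure by 0.20 × 50 = 10 points if the two places differ by 50 points, but by only 0.20 × 10 = 2 points if they differ by 10.

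**Step 5. Tabulating by profession.** Under the Step 4 assumption, a table by Section A item 6 returns 20% for non-laboratory staff and 80% for laboratory staff, and the mix effect is gone. The ambiguity in Step 3 remains within each profession. If half of the doctors and nurses had the laboratory in mind, their own row would again read 50% for all three pairs. Profession says who answered, not which place was rated.

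**Step 6. Other items.** Item 9 can name a place, but only when a respondent reports a problem and chooses to write. Silence there is not a rating of adequate, so it cannot supply the two missing frequencies.

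**The case against.** The strongest reply is that profession is already on the form. If each group rates its own workplace, a simple cross-tabulation separates the clinic from the laboratory, and nothing in Section 5.4 requires a single pooled figure. This stands as far as it goes: a reader might infer that the result must move with the staff mix, and the documents do not support that once results are shown by profession. It rests, however, on the assumption that doctors, nurses and pharmacists had only the clinic in mind, which the form neither asks nor records. It would also leave the laboratory to be judged by whatever laboratory staff are in a sample of "Professionals working with SCD patients (mainly doctors and nurses" and discard the view of clinicians who depend on it.

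Second, the study is mixed-method with thematic analysis, and item 9 directly follows items 7 and 8. The free text may well show where problems lie. So it would be too strong to say that Annex II as a whole cannot locate a shortage; the limitation belongs to item 7.

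Third, the effect may be small beside sampling error. With 30 staff per centre and proportions near 40%, the 95% half-width for a difference between two centres is 1.96 × √(2 × 0.4 × 0.6 / 30) ≈ 25 points, larger than the assumed 10-point shift in Step 4. The protocol plans no test between centres. This is fair and bears on severity. It does not help the respondent with a mixed view, who still has no accurate box.

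**Conclusion.** Item 7 is double-barrelled, and by itself it cannot show whether the clinic or the laboratory is short. That follows from the wording alone and needs no numerical assumption. The size of any distortion cannot be computed from the protocol: it depends on how far the two places differ and on which place respondents had in mind. The percentages in the working are illustrations. The severity is minor: one item of 18 in a descriptive pilot, with no stated decision resting on it.

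Three wider readings are tempting and should not be drawn.

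- Item 8 does not share the defect. It is a single global question, and splitting it would be a matter of preference.
- Items 7 and 8 are not the only closed measures of facility need. The reasons listed after item 17 include poor equipment, although only dissatisfied staff are asked and no place is named.
- The separate laboratory items in the patient form (Annex I, items 12 to 14) are not a lost comparator. They ask about services, communication and waiting, not the number of facilities, and would not match item 7 even after a split.

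**What to change.** Split item 7, and only item 7, into (a) the clinic and (b) the laboratory. Keep the existing five answers for each and add a don't know/not applicable option, so that staff are not pushed to rate a place they do not use. Report (a) and (b) separately, each by profession from Section A item 6, with the number choosing the added option.

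The cost is one extra line on the staff form. The sample size and the other items do not change. If forms have already been completed, the same split can be made for the wider survey, and the pilot's item 7 should be reported as a combined rating whose place is not known.
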